## 9.1.13 Contraception and Pregnancy Avoidance Procedure

From signing of informed consent, throughout the duration of the study, and for 14 days after last dose of study medication, female subjects of childbearing potential\* who are sexually active with a nonsterilized male partner\*\* must use adequate contraception. In addition they must be advised not to donate ova during this period.

\*Females NOT of childbearing potential are defined as those who have been surgically sterilized (hysterectomy, bilateral oophorectomy or tubal ligation) or who are postmenopausal (eg, defined as at least 1 year since last regular menses with an FSH >40 IU/L or at least 5 years since last regular menses, confirmed before any study medication is implemented).

\*\*Sterilized males should be at least 1 year postvasectomy and have confirmed that they have obtained documentation of the absence of sperm in the ejaculate.

An acceptable method of contraception is defined as one that has no higher than a 1% failure rate. In this study, where medications and devices containing hormones are included, the only acceptable methods of contraception are:

**Table 9.b** Acceptable Methods of Contraception

Barrier Methods (a)	Intrauterine Devices (IUDs)	Hormonal Contraceptives
Male condom PLUS spermicide.	Copper T PLUS condom or spermicide.	

 Implants.

 Hormone shot/injection.

 
Cap (plus spermicidal cream or jelly) PLUS male condom and spermicide.
 
	
 
Progesterone T PLUS condom or spermicide.
 
	

Combined pill.

Minipill.

 
Diaphragm (plus spermicidal cream or jelly) PLUS male condom and spermicide.
 
		

Patch.

Vaginal ring PLUS male condom and spermicide.

IUD=intrauterine device.

Subjects will be provided with information on acceptable methods of contraception as part of the subject informed consent process and will be asked to sign a consent form stating that they understand the requirements for avoidance of pregnancy and donation of ova during the course of the study.

During the course of the study, regular serum and urine hCG pregnancy tests will be performed for women of childbearing potential only, and subjects will receive continued guidance with respect to the avoidance of pregnancy as part of the study procedures (Appendix A). In addition to a negative serum hCG pregnancy test at Screening, subjects also must have a negative urine hCG pregnancy test prior to dispensing of study medication at Visit 2.

## 9.1.14 Pregnancy

If any subject is found to be pregnant during the study she should be withdrawn and any sponsor-supplied drug (lubiprostone or matching placebo) should be immediately discontinued.

If the pregnancy occurs during administration of active study medication, eg, after Visit 2 or within 14 days of the last dose of active study medication, the pregnancy should be reported immediately, using a pregnancy notification form, to the contact listed in Section 1.0.

Should the pregnancy occur during or after administration of blinded drug, the investigator must inform the subject of their right to receive treatment information. If the subject chooses to receive unblinded treatment information, the individual blind should be broken by the investigator. Subjects randomized to placebo need not be followed.

If the female subject and/or female partner of a male subject agrees to the primary care physician being informed, the investigator should notify the primary care physician that the subject/female partner of the subject was participating in a clinical study at the time she became pregnant and provide details of treatment the subject received.

a) Barrier methods: to be used each time the subject has intercourse.

All pregnancies in subjects on active study drug including comparator will be followed up to final outcome, using the pregnancy form. Pregnancies will remain blinded to the study team. The outcome, including any premature termination, must be reported to the sponsor. An evaluation after the birth of the child will also be conducted (first well baby visit).

#### 9.1.15 Documentation of Screen Failure

Investigators must account for all subjects who sign informed consent.

If the subject is found to be not eligible at this visit, the investigator should complete the eCRF. The IWRS should be contacted as a notification of screen failure.

The primary reason for screen failure is recorded in the eCRF using the following categories:

- PTE/AE.
- Did not meet inclusion criteria or did meet exclusion criteria.
- Significant protocol deviation.
- Lost to follow-up.
- Voluntary withdrawal (specify reason).
- Study termination.
- Other (specify reason).

Subject numbers assigned to subjects who fail screening should not be reused.

#### 9.1.16 Documentation of Randomization

Only subjects who meet all of the inclusion criteria and none of the exclusion criteria are eligible for randomization into the Double-Blind Treatment Period.

If the subject is found to be not eligible for randomization, the investigator should record the primary reason for failure on the applicable eCRF.

If the subject is found to be eligible the subject will be randomized to either lubiprostone or placebo using IWRS. Instructions on accessing and using the IWRS will be provided in a separate manual. Blinded details of subject treatment allocation (MED ID numbers) will be provided via the IWRS.

## 9.1.17 Subject Diary

The study diary will be a paper diary distributed to each subject on Study Days -15, -1, 8, and 15.

Subjects will be instructed to record in the diary every day, including the morning of Visit 1 (Day -15, the first day of the Screening Period). Subjects will continue to record their defecation behavior in the diary to confirm he/she has constipation. Use of all laxatives will be stopped at

the beginning of the Screening Period (Visit 1), and subjects will be instructed not to change their diets or lifestyle habits during the study.

The study diary will be collected and reviewed for completeness on Study Days -1, 8, 15, 29 and any unscheduled visit. The authorized study personnel will transcribe all data collected from the diary into the eCRF. All information collected from the diary will be analyzed for primary and secondary endpoints in the study.

All subjects should be instructed about diary completion at every study visit. Documentation that subjects are appropriately instructed (and re-instructed as necessary) on diary completion should be recorded in the subject's source notes.

Subjects who are not consistent or thorough with study diary completion may receive phone reminders if deemed necessary by the investigators. The authorized study personnel providing phone reminders must document the phone contact process in the subject's source notes.

A sample of the diary is located in Appendix E; it provides a sample of the types of questions that the diary asks as a way of helping the subject to record defecation behavior.

## 9.2 Monitoring Subject Treatment Compliance

Subjects will be required to bring study medication bottles/ unused medications to each dispensing site visit.

If a subject is persistently noncompliant with the study medication, it may be appropriate to withdraw the subject from the study. All subjects should be reinstructed about the dosing requirement during study contacts. The authorized study personnel conducting the re-education must document the process in the subject source records.

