Note: If the subject is found to be pregnant, the subject must be withdrawn immediately. The procedure is described in Section 9.1.14.

- 7. Lack of efficacy. The investigator has determined that the subject is not benefiting from investigational treatment; and, continued participation would pose an unacceptable risk to the subject.
- 8. Unblinding of subject treatment.
- 9. Other.

Note: The specific reasons should be recorded in the "specify" field of the eCRF.

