# 7.6 Procedures for Discontinuation or Withdrawal of a Subject

The investigator may discontinue a subject's study participation at any time during the study when the subject meets the study termination criteria described in Section 7.5. In addition, a subject may discontinue his or her participation without giving a reason at any time during the study. Should a subject's participation be discontinued, the primary criterion for termination must be recorded by the investigator. In addition, efforts should be made to perform all procedures scheduled for the Early Termination Visit, with a follow up telephone contact 14 days later. Discontinued or withdrawn subjects will not be replaced.

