# 8.5 Unblinding Procedure

The investigational drug blind shall not be broken by the investigator unless information concerning the investigational drug is necessary for the medical treatment of the subject. In the event of a medical emergency, if possible, the medical monitor should be contacted before the investigational drug blind is broken to discuss the need for unblinding.

For unblinding a subject, the investigational drug blind can be obtained by the investigator, by accessing the IWRS.

The sponsor must be notified as soon as possible if the investigational drug blind is broken. The date, time, and reason the blind is broken must be recorded in the source documents and the same information (except the time) must be recorded on the eCRF.

If any site personnel are unblinded, investigational drug must be stopped immediately and the subject must be withdrawn from the study.

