### Full Analysis Set

This will consist of all subjects randomized to receive study treatment whether or not they received treatment. Subjects will be assigned to the randomized treatment group regardless of treatment received.

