## 13.1.3 Efficacy Analysis

Two-sided tests at a significance level of  $\alpha$ =5% will be used throughout unless otherwise stated. The null hypothesis is that lubiprostone is equal to placebo against the alternative that lubiprostone is different to placebo. All analyses will be performed using the FAS. Analyses specified for the PP are to be regarded as supportive evidence. There will be no adjustment for multiplicity.

All efficacy endpoints will be summarized by treatment and visit. If baseline measures are also defined and collected for an efficacy endpoint then change from Baseline at each visit will also be presented by summary statistics by treatment and visit. Baseline is defined as the last recorded measurement prior to treatment. For parameters based on diary data, baseline values will be derived using the data from the Screening Period.

Centers may be pooled geographically if necessary for analysis purposes.

The LOCF technique will be used to impute missing values. For a given subject, the most recent nonmissing treatment-period data point will be carried forward to the subsequent week where data are missing. Supportive analyses will be conducted without missing value imputation (ie, without LOCF) and with a 'worse-case' scenario where missing values are assigned the worst case values recorded in the study by any subject for that endpoint at that time.

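### Ending data collection for non-adherent or unblinded subjects leaves Weeks 2-4 to LOCF; asking them to continue the diary to Day 29 is a cheap improvement

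*Protocol*

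**What the plan says.** **Leaving the study.** For persistent non-adherence, Protocol 9.2 says "it may be appropriate to withdraw the subject from the study". After unblinding of any site personnel, Protocol 8.5 says "investigational drug must be stopped immediately and the subject must be withdrawn from the study", and Protocol 7.5 lists "Unblinding of subject treatment" among the reasons for discontinuation. In both places the subject leaves the study, not only the study drug.

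**What is collected afterwards.** Protocol 7.6 says "efforts should be made to perform all procedures scheduled for the Early Termination Visit, with a follow up telephone contact 14 days later". No section asks a withdrawn subject to go on with the diary.

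**What is analysed.** The FAS contains all randomised subjects: "Subjects will be assigned to the randomized treatment group regardless of treatment received". For missing weeks, Protocol 13.1.3 says "the most recent nonmissing treatment-period data point will be carried forward to the subsequent week where data are missing". SAP 7.8.2 carries the Week 1 SBM frequency into a missing Week 2 and applies LOCF to straining, stool consistency and abdominal symptoms.

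**Planned support.** Protocol 13.1.3 also plans analyses without imputation and with worst-case values. The SAP spells out the worst case for Weeks 1 and 2 and does not restate the no-imputation analysis.

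**The concern.** Neither non-adherence nor unblinding makes it impossible to record bowel movements. The diary, the visits and the staff are already in place. Yet once a subject is withdrawn from the study for either reason, the later outcomes are not collected, and an earlier week stands in for them in an analysis set meant to reflect everyone as randomised. Non-adherence may follow poor tolerability or little benefit, so these gaps may be informative.

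At stake is the reading of Weeks 2-4. Protocol 6.2 uses later SBM frequency and the weekly responder rates to support a continuing effect. The responder definition (Protocol 9.1.7.6, SAP 7.8.2) makes a dropout a non-responder by reason of dropping out only if the reason was lack of efficacy. A subject withdrawn for non-adherence or unblinding is not caught by that clause, so a carried-forward frequency of 3 or more could keep responder status.

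**Working it through.** **1. Does the diary stop?** Three places have to be read together.
- Protocol 9.3.4: the Early Termination Visit takes place within 1 week of discontinuation.
- Protocol 9.3.5: the Follow-up Period starts the day after that visit.
- Appendix A, footnote (j): the diary runs to Day 29, with none in the Follow-up Period.

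So entries may continue for up to about a week after discontinuation and then end. This is an inference from the schedule, not an explicit sentence.

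**2. The plan's own figure.** Protocol 13.3 gives Week 1 means (SD) of 4 (2.7) on placebo and 5.9 (4) on lubiprostone, 90% power and two-sided alpha 0.05.
- SD = √((2.7² + 4²)/2) = 3.412; difference = 5.9 − 4.0 = 1.9.
- A two-sample t-test needs 68.76 per arm; × π/3 for the Wilcoxon test gives 72.01, rounded up to 73, total 146. This matches the plan.
- Allowing for 3% dropout: 146/0.97 = 150.5, so 151 against the stated 150, a trivial difference.

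This calculation concerns Week 1, so nothing below changes it.

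**3. Illustration for Weeks 2-4.** Assumptions: the Week 1 means persist; withdrawn subjects were average before leaving; a fraction w leaves by these routes; their true off-drug mean equals placebo (4.0). The documents give no w, so 1% to 10% is shown.
- Difference under LOCF: 5.9 − 4.0 = 1.90.
- Difference if observed: (1 − w)·5.9 + w·4.0 − 4.0 = 1.9·(1 − w).
- Overstatement: 1.9·w.

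**4. Extreme one-arm scenario.** Only lubiprostone subjects leave, and they fall to 1.5 SBMs/week, the baseline median in the two US studies (Protocol 4.1.4). The observed difference would be 1.9 − (5.9 − 1.5)·w = 1.9 − 4.4·w.

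| w | Subjects per arm of 75 | Step 3: difference (overstatement) | Step 4: difference (overstatement) |
|---|---|---|---|
| 1% | 0.75 | 1.88 (0.02) | 1.86 (0.04) |
| 2% | 1.5 | 1.86 (0.04) | 1.81 (0.09) |
| 5% | 3.75 | 1.81 (0.10) | 1.68 (0.22) |
| 10% | 7.5 | 1.71 (0.19) | 1.46 (0.44) |

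If both arms lose the same fraction and both fall to 1.5, the overstatement is w·(4.4 − 2.5) = 1.9·w, the same as step 3. If only placebo subjects left and fell to 1.5, LOCF would understate the difference by 2.5·w, or 0.125 at 5%. So the direction also depends on who leaves.

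**5. Timing.** Capsules are checked on Days 8, 15 and 29 (Appendix A). Persistent non-adherence can hardly be established before Day 8, and Day 15 is more plausible. In that case Week 2 is observed and only Weeks 3-4 are carried. Week 1 is affected only if a subject leaves during Week 1. With at least 4 days the rate is scaled to 7 days; with fewer, the SAP imputes.

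**The case against.** The case for leaving the text alone has real force.

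- **Mitigation is planned.** A Week 2-4 effect that rested on LOCF should show up against the no-imputation and worst-case results. This stands as mitigation. Neither analysis uses observed outcomes after withdrawal, and the SAP only partly carries them over.
- **The routes may be rare.** Section 9.2 is permissive. Section 8.5 allows the investigator to break the blind only when the subject's medical treatment needs it. This stands: non-adherence is probably the larger route, and no rate is known for either.
- **The mean shift is an indirect measure.** The planned tests are rank-based. A subject who stops because of little benefit carries forward a low value, which shrinks the overstatement. This also stands.
- **Unblinded diary entries may be coloured by knowledge of treatment.** That is a reason to flag them, not to leave them uncollected.

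Stronger readings are tempting but not supported. A reader might infer that the all-randomised FAS contradicts the withdrawal rules. It does not: the FAS defines who is analysed, not what is collected. A reader might infer that on-drug values systematically replace off-drug ones. That is too loose: a non-adherent subject's carried week may be partly off drug, placebo subjects carry placebo values, and with no treatment value the SAP uses baseline for SBM frequency or the worst score for the symptom scales. A reader might also quote an inflation of 12% (0.22/1.9). That needs 5% withdrawal in one arm, none in the other, and a full fall from the mean response to baseline.

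**Conclusion.** The concern holds as a worthwhile, low-cost improvement limited to secondary endpoints at Weeks 2-4. Following the plan as written gives up outcomes that could be obtained and fills them by LOCF.

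The size cannot be determined from the documents. On the step 3 assumptions it is small at 1-2% withdrawal and becomes noticeable only towards 5-10%; the larger one-arm figures are an outer bound for illustration, not an expectation. The documents do not support a claim that the primary result is at risk.

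There is also a point of consistency. Section 7.6 ties discontinuation by the investigator to the criteria in 7.5. Those criteria do not name non-adherence, and their protocol-deviation category applies only where continuing poses an unacceptable health risk. Section 9.2 carries no such condition. These passages must be reconciled, or sites will apply 9.2 differently.

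**What to change.** 1. In Protocol 9.2 and 8.5, state that non-adherence or unblinding is not by itself a reason to end data collection. Ask such subjects to continue the diary and the remaining visits (Visits 3-5) to Day 29 unless they withdraw consent.
2. In Protocol 13.1.3 and SAP 7.8, state that these observed data are used in the FAS, with LOCF kept for weeks that are truly missing. Flag entries made after unblinding.
3. Restate the no-imputation analysis in the SAP, and name Weeks 3 and 4 explicitly for the worst-case analysis.
4. Reconcile 9.2 with 7.5 and 7.6.

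Leave every decision on study drug as the protocol now has it; the change concerns data collection only.

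The cost is a short wording amendment and some further diary collection within the existing schedule. The downside is that some off-drug weeks enter the analysis and slightly dilute the Week 2-4 effects, which is consistent with an analysis of all subjects as randomised.

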#### 9.3 Schedule of Observations and Procedures

The schedule for all study-related procedures for all evaluations is shown in Appendix A. Assessments should be completed at the designated visit/time point(s). The recommended visit windows for Visits 2, 3, 4, and 5 are within 2 days of the required visit.

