Approximately 150 subjects whose constipation is confirmed during the Screening Period will be randomized in the Double-Blind Treatment Period to receive either lubiprostone or matching placebo BID. Others whose constipation does not satisfy the criteria during the 14-day Screening Period or those who receive a rescue medication within 24 hours prior to the first dose on Day 1 are ineligible for randomization in the Double-Blind Treatment Period and therefore will be excluded from the study. Subjects who satisfy the inclusion criteria and do not meet the exclusion criteria are randomized to 1 of the treatment groups in the order of the number assigned. Approximately 150 subjects with CIC will be randomized to 2 groups: active treatment or placebo in a 1:1 ratio (75 subjects each) in a double-blinded manner.

[figure not shown]
Subjects will be instructed to take 1 capsule BID, orally, at the same time of day, preferably in the morning with breakfast and in the evening with dinner. Subjects are to begin their study drug treatment in the morning with breakfast following Visit 2.

Subjects will return to the study site on approximately Study Days 8, 15, and 29 during the 4 weeks of double-blind treatment and will be followed for an additional 2 weeks during the Follow-Up Period, in which no treatment will be administered.

At the investigator's discretion, with consideration to subject's bowel movement frequency and consistency, dose adjustments (dose reduction) may be made in a double-blind manner. Dose adjustment should be documented in the subject's source notes. Procedure for reduction of study drug dose due to Adverse Events is described in Section 7.7.

Subjects who withdraw prematurely will be seen within 1 week of discontinuation for an Early Termination Visit. A schematic of the study design is included as Figure 6.a. A schedule of assessments is listed in Appendix A.

Figure 6.a Schematic of Study Design

Note: Randomization occurs on Day -1 of the Screening Period. The first dose of study drug is administered the next day, on Day 1 of the Double-Blind Treatment Period.

Note: There is no treatment during the Follow-up Period.

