# 8.1 Study Medication and Materials

# 8.1.1 Dosage Form, Manufacturing, Packaging, and Labeling

In this protocol, the term study medication refers to all or any of the drugs defined below.

- Lubiprostone 24 µg capsules.
- Placebo capsules to match lubiprostone 24 μg.

Investigational material is encapsulated in clear orange soft gelatin capsules and packaged into 60 count high-density polyethylene (HDPE) bottles, including a rayon filler, induction sealed and closed with a child-resistant cap. Each bottle contains enough capsules to treat subjects for 28 days + a 2-day window during the Double-Blind Treatment Period, and will be labeled with a single-panel label including pertinent study information. As this study is double-blind, all study medication will be packaged, labeled, and dispensed in a blinded manner.

The bottle will contain an unique medication identification (MED ID) number and will be dispensed via the Interactive Web Response System (IWRS), with 1 bottle dispensed per subject.

An IWRS program will be used to manage inventory, assist the site in dispensing the proper investigational drug to the subjects, record accountability and support the return to sponsor or designee of these investigational drugs after study completion.

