# 8.2 Investigational drug Assignment and Dispensing Procedures

The investigator or investigator's designee will access the IWRS at Screening/ Visit 1 to obtain the subject study number.

After study eligibility is confirmed (ie. at Visit 2), the investigator or the investigator's designee will utilize the IWRS to randomize the subject into the study. During this contact, the investigator or designee will provide the necessary subject-identifying information, including the

subject number assigned at Screening. The MED ID number of the investigational drug to be dispensed will then be provided by the IWRS.

If the investigational drug is lost or damaged, the site can request a replacement from IWRS. (Refer to IWRS manual provided separately.)

If a dose was missed, the subject is to leave the capsule in the bottle and resume regular administration at the next scheduled dose time. The subject is instructed to note the missing dose in the daily diary.

Instructions for subjects on how to store investigational drug will be provided by the investigator or investigator's designee.

Unused medication should be returned at Visit 5.

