## Appendix A Schedule of Study Procedures

	Screening	Randomization  Day -1 (a)	Treatment			Follow-up Period	
Study Day/Week	Day -15		First Dose Day 1 (b)	Week 1	Week 2	Final Visit or Early Termination Visit Week 4 (c)	Follow-up Phone Contact Week 6 (0)
Visit Windows (Days): (+/- 2 days)	-15 to -1	-1	1	8	15	29	43
Visit Number:	1	2	N/A	3	4	5	N/A
Informed consent	X						
Demographics and medical history (d)	X						
Inclusion/exclusion criteria (e)	X	X					
Medication history	X						
Physical examination	X					X	
Vital signs (f)	X	X				X	
Weight and height (g)	X					X	
Concomitant medications	X	X	X	X	X	X	X
Concurrent medical conditions	X						
Clinical laboratory tests (h)	X					X	
Pregnancy test (i)	X	X				X	
Urine drug screen	X						
Access IWRS for Subject ID/MED ID/Subject Status	X	X				X	
Dispense investigational drug		X					
Distribute rescue medications prescription as necessary	X	X		X	X		
Drug return/accountability/compliance				X	X	X	
Dispense study diary	X	X		X	X		
Efficacy:		ı				ı	I
Abdominal symptom assessment review (by diary)		X		X	X	X	
PAC-QOL		X			X	X	
Use of rescue medication (by diary)		X		X	X	X	
Diary-keeping by subjects (j)	X	X	X	X	X	X	
Diary collection/ compliance check (k)		X		X	X	X	
Safety:	 						
Guidance on avoidance of pregnancy and ova donation	X	X		X	X	X	
Pretreatment adverse events (1)	X	X					
Adverse events (m)			X	X	X	X	X
Dose reduction (optional) (n)				X	X		
Phone interview							X
	 			 	 		

Footnotes are on last table page.

N/A= not applicable.

- (a) Subjects will be randomized on Day -1, the last day of the Screening Period. They will also receive their bottle of dispensed investigational study drug on Day -1, although they will be instructed to take the first dose the next day, on Day 1.
- (b) Day 1 is the first day of study drug administration. Subjects are to take 1 capsule of lubiprostone 24 μg or placebo with 240 mL of water in the morning with breakfast, and again in the evening with dinner. Repeat this regimen for 4 weeks.
- (c) Conduct Final Visit procedures for subjects discontinued early per Section 7.6. Subjects who withdraw prematurely should return within 1 week of discontinuation for an Early Termination Visit.

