- (d) Includes the results at Screening for IBS. The results of enema X-ray examination or total colonoscopy performed in the past 2 years are referred to in order to determine organic disorders that can be ruled out. For subjects who have no history or show no current evidence of weight loss, anemia, or rectal bleeding, the examination results of the past 3 years may be used to rule out organic disorders.
- (e) Subject eligibility is to be reconfirmed for all criteria on Day -1, Randomization Day, including diary data.
- (f) Vital signs=blood pressure (systolic and diastolic), body temperature, and pulse rate.
- (g) Height will be measured at Visit 1 and weight will be measured at Visit 1 and 5.
- (h) Hematology: hemoglobin, hematocrit, RBC, WBC with differential, platelets, MCV, MCH, RDW.

Serum chemistry: ALP, Albumin, ALT, AST, total bilirubin, direct bilirubin, total protein, total cholesterol, triglyceride, glucose, creatinine, BUN, creatine kinase, uric acid, GGT, LDH, Na, K, Cl, Ca, P, Mg, (TSH [performed to exclude hypothyroidism] and CRP levels are measured at Visit 1 only).

Urinalysis: pH, specific gravity, protein, glucose, occult blood, urobilinogen, bilirubin, ketone and leukocyte esterase. Microscopic analysis (only if positive dipstick results).

- (i) In women of childbearing potential only. Serum hCG pregnancy test conducted at Screening and at Final Visit (Early Termination Visit), and urine hCG pregnancy test conducted at Visit 2.
- (j) Diary-keeping by subjects will be continuous from Day -15 throughout the Screening Period and the Double-Blind Treatment Period to Day 29 (Final Visit). There will be no diary-keeping in the Follow-up Period.
- (k) Subjects who are not consistent or thorough with study diary completion may receive phone reminders if deemed necessary by the investigators. The authorized study personnel providing phone reminders must document the phone contact process in the subject's source notes.
- (1) Pretreatment adverse events: an adverse event in subjects who have signed informed consent to participate in the study that occurs prior to administration of any study medication; the event does not necessarily have to have a causal relationship with study participation. The pretreatment adverse events are assessed from Day -15 to hour 0 on Day 1, when study drug is administered.
- (m) Pregnancy reporting in Follow-Up Period occurs at 2 weeks after the last dose of study drug.

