## Weekly Abdominal Symptoms Score (Bloating and Discomfort) (Week 1, 2, 3, and 4)

The abdominal symptom score should be completed by patients in their diary, every 7 days on the last day of each treatment week upon waking in the morning. Patients should indicate the degree of abdominal bloating and discomfort experienced over the past week.

Abdominal Bloating	0 = None: No abdominal distension	
	1 = Mild: Slight abdominal distension	
	2 = Moderate: Abdominal distension clearly felt	
	3 = Severe: Severe abdominal distension	
	4 = Very severe: Extremely strong abdominal distension	
Abdominal Discomfort	0 = None: No abdominal discomfort	
	1 = Mild: Slight abdominal discomfort	
	2 = Moderate: Abdominal discomfort clearly felt	
	3 = Severe: Abdominal discomfort with pain	
	4 = Very severe: Abdominal discomfort with severe pain	

The abdominal symptoms (bloating and discomfort) will be analyzed separately by van Elteren tests, stratified by center, at Weeks 1, 2, 3, and 4. A related 95% confidence interval and point estimate will be provided for the treatment difference; the confidence interval will be estimated by inverting the hypothesis test.

Additionally a cumulative logistic regression model will be used with treatment and center as factors as a sensitivity analysis. The estimated odds ratio and associated 95% CI will also be presented to aid interpretation of the clinical effect. The interaction between treatment and center will also be examined in a separate model.

If the assessment ratings are missing, then the LOCF method will impute the value from the value used for the most recent week. For Week 1 analysis where there is no value to carry forward then a value of 4 will be assumed. This assumption will be carried into later weeks if LOCF does not provide an estimate.

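### A Visit 5 held in window on Day 27 closes the diary one day before the Week 4 bloating and discomfort score is due and leaves about five days of Week 4

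*Protocol*

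**What the plan says.** **Visits.** Protocol 6.1: "Subjects will return to the study site on approximately Study Days 8, 15, and 29 during the 4 weeks of double-blind treatment". Protocol 9.3: "The recommended visit windows for Visits 2, 3, 4, and 5 are within 2 days of the required visit". The window row of Appendix A gives the direction: "Visit Windows (Days): (+/- 2 days".

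**Weekly abdominal score.** Bloating and discomfort at Weeks 1 to 4 are secondary endpoints (protocol 5.2.2.1, SAP 5.0). SAP 7.8.2 has the subject rate them "every 7 days on the last day of each treatment week upon waking in the morning". A missing rating takes the value used for the most recent week.

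**Diary.** Protocol 9.1.17: "The study diary will be collected and reviewed for completeness on Study Days -1, 8, 15, 29 and any unscheduled visit". During treatment a new diary is issued only at Visits 3 and 4 (9.3.3). Appendix A note (j) has the diary kept "throughout the Screening Period and the Double-Blind Treatment Period to Day 29 (Final Visit", with none in follow-up. Follow-up starts the day after the Final Visit (9.3.5).

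**Drug.** Protocol 8.1.1 supplies "enough capsules to treat subjects for 28 days + a 2-day window", in a 60-capsule bottle. Protocol 8.2: "Unused medication should be returned at Visit 5".

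**Week 4 analysis.** Weeks are 168-hour intervals counted from the Day 1 morning dose (SAP 7.1). Weekly SBM frequency is 7 times the SBM count divided by the days in study that week (SAP 7.8.1), and at least 4 days are needed (SAP 7.8). A responder with a rate of at least 3 but below 4 is moderate; at 4 or more the responder is full (SAP 7.8.2).

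**The concern.** The visit window and the scoring day were set separately, and they collide at the last visit. The early edge of the Visit 5 window falls one day before the Week 4 score is due, and no diary exists after that visit to hold the score. A subject and a site that follow the protocol exactly can therefore lose a secondary endpoint value.

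The analysis does not show the loss. The Week 3 rating is reported as Week 4, and the shortened Week 4 passes the 4-day minimum, so it is not counted as missing. At stake are the Week 4 bloating and discomfort scores and, to a lesser degree, the Week 4 SBM frequency and responder category. The plan allows for a late visit through the spare capsules. It says nothing about an early one.

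**Working it through.** No figure in the plan measures this effect, and the sample size calculation (Week 1 SBM frequency) does not bear on it. The one related figure, the drug supply, reproduces: 60 capsules / 2 per day = 30 days = 28 + 2.

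**1. Earliest visit against scoring day.** Score due on Day 7 × week number.
- Visit 3: 8 − 2 = Day 6; Week 1 score due Day 7. A new booklet is issued.
- Visit 4: 15 − 2 = Day 13; Week 2 score due Day 14. A new booklet is issued.
- Visit 5: 29 − 2 = Day 27; Week 4 score due Day 28. No booklet is issued.

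Only at Visit 5 does the score have nowhere to go.

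**2. Share of Week 4 observed.** Week 4 runs from hour 504 to hour 672 after the first dose, that is from the morning of Day 22 to the morning of Day 29. Assume a first dose at 08:00 and visits between 09:00 and 17:00. Hours observed = (visit day − 22) × 24 + (visit hour − 8), capped at 168.

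| Visit 5 on | Day 28 waking score before collection | Hours of 168 | Days of 7 | Lost |
|---|---|---|---|---|
| Day 27 | no | 121 to 129 | 5.0 to 5.4 | 23% to 28% |
| Day 28 | yes | 145 to 153 | 6.0 to 6.4 | 9% to 14% |
| Days 29 to 31 | yes | 168 | 7 | none |

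For example, Day 27 at 09:00 gives 5 × 24 + 1 = 121 hours, and 1 − 121/168 = 28%.

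**3. Effect on the responder category.** Rate = 7 × SBMs / days.
- 7 days: 3 SBMs give 3.0, moderate.
- 5 days: 2 SBMs give 14/5 = 2.8, non-responder; 3 SBMs give 21/5 = 4.2, full responder. No whole count gives a rate from 3 to below 4.
- The SAP does not say whether days are counted whole or in fractions. With fractions, 3 SBMs fall below 4 once the denominator exceeds 21/4 = 5.25 days, so a late-afternoon Day 27 visit could still give a moderate responder (21/5.375 = 3.9).

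**4. Treatment length.** Drug is returned at Visit 5 and follow-up is untreated. If dosing ends at a Day 27 visit, 26 × 2 = 52 capsules have been taken, or 53 with that morning's dose, against 28 × 2 = 56 planned.

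**The case against.** **The text points to Day 29.** The windows are only recommended. Protocol 9.3.4 places the Final Visit at the end of Week 4, and note (j) and Appendix E run the diary to Day 29. This is true, but nothing bars Day 27 or keeps the diary open after an early visit, so the passages disagree with one another.

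**Only one day of five is affected.** Of Days 27 to 31, only Day 27 precedes the score. This stands, and it limits the point. (If the last day of Week 4 were read as the morning of Day 29, where the 168 hours end, a Day 28 visit would lose the score too.)

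**A rating might be entered a day early.** The protocol says only that symptoms are scored weekly (9.1.7.5). The day rule is in the SAP, and the booklet layout is not shown. A site might accept a Day 27 rating as Week 4, but no passage provides for it.

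**SBM frequency is handled.** It is pro-rated from more than 4 days. This stands: the frequency is less precise, not lost. Protocol 13.1.3 also plans supportive analyses without LOCF, which would expose carried-forward scores, although the SAP does not repeat this for the abdominal scores.

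**Visits 3 and 4.** A reader might infer that Week 1 and Week 2 scores are lost in the same way. The documents do not support that. A new booklet is issued at both visits, diary-keeping is continuous, and SAP 7.1 assigns each score to the week recorded in the diary. Bowel movements are assigned by date and time, so the Week 1 primary endpoint is untouched.

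**Conclusion.** The concern holds as a minor point, confined to secondary endpoints at Week 4. A subject whose Visit 5 falls on Day 27 is in window, has no Day 28 bloating or discomfort score, and is analysed with the Week 3 value. That subject's Week 4 SBM frequency rests on about 5.0 to 5.4 of 7 days, and with a 5-day denominator the moderate-responder category is empty. A Day 28 visit keeps the score and loses about 9% to 14% of the week. Later visits lose nothing.

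This rests on three assumptions: the last day of Week 4 is Day 28, no rating is entered before it is due, and dose and visit times are about as assumed above.

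Two stronger readings are tempting and are not supported. One puts a number on the subjects affected. Uniform attendance over the five permitted days, with all 150 subjects reaching Visit 5, would give 150 / 5 = 30 on Day 27, but the documents give no distribution of visit days, so the number cannot be computed. The other says that subjects who feel unwell come early and so bias the comparison between arms. Nothing in the documents shows that early attendance would differ by arm.

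**What to change.** 1. In protocol 9.3 and the Appendix A window row, set the Visit 5 window to 0/+2 days, so that Visit 5 is not held before Day 29. This agrees with 9.3.4, note (j) and Appendix E. Every Week 4 score then falls due before collection, and Week 4 is observed for 168 of 168 hours (on the timing assumed above).
2. Leave the Visit 3 and Visit 4 windows as they are. State either that no booklet is collected before that week's abdominal score has been entered, or that a score falling due after an early Visit 3 or 4 is entered in the new booklet under its own week.
3. Reconcile the visit window, the return of drug at Visit 5 and the stated 28-day treatment period.

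Cost: one line in 9.3 and one entry in Appendix A, a sentence on the booklets, and the reconciliation. Sites lose two scheduling days before Visit 5. No visits, subjects or drug are added; the existing bottle holds 30 days of capsules.
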